### Randomisation

Women with prior GDM are the unit of randomisation. Randomisation was stratified on Centres: Odense, Aarhus, Copenhagen sites, i.e. for each centre, random allocation is performed in a 2:1 ratio to the intervention (2/3 of participants) or usual care (1/3 of participants). Randomisation was in random blocks of sizes 6/9/12/15, which ensures that allocation to intervention or usual care is unpredictable for recruiters and that the cumulative ratio of participants included to intervention vs. usual care is close to 2:1 throughout the inclusion period at each hospital. Randomisation will not be based on stratification for baseline variables. Details of the randomisation method are held securely within the files of the statistician. The randomisation procedure was generated by a statistician ([name]) prior to the commencement of recruitment. The allocation sequence will be implemented using the REDCap (Research Electronic Data Capture) electronic system. The randomisation process is described in full within the clinical trial protocol (2).

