## **Section 3: Statistical principles**

### **Confidence intervals and p-values**

All relevant statistical tests will be based on two-sided p-values using a 5% significance level. P-values will be reported for estimates related to the primary outcome and secondary outcomes. Wald-based 95% confidence intervals will be given for all reported estimates.

**Primary outcomes:** We will employ a hierarchical testing procedure with two separate hierarchies (one hierarchy for each of the two primary outcomes) to control the type 1 error rate for tests. Thus, if a test fails to confirm a given hypothesis, all subsequent tests within the specific hierarchy will be considered as tertiary outcomes. If the null hypothesis is rejected at the  $\alpha$  level of 0.05 (two-sided), i.e., the p-value of the null hypothesis test is  $< 0.05$ , statistical significance will be claimed. In order for the results to be declared in accordance with the hypothesis, the size of the estimated mean effect of the primary outcome, its direction, and the 95% confidence intervals will be required to support the tested hypothesis.

**Secondary outcomes:** Secondary outcomes within the clinical, metabolic and behavioural domains will belong to the hierarchy for BMI. Secondary outcomes within the quality of life & mental health domain will be embedded in the Quality of Life (SF-12 mental component) hierarchy. We will control for multiplicity using the Holm-Bonferroni method.

**Tertiary outcomes:** These outcomes are considered descriptive/explorative meaning no definite inferences can be made. Therefore, we will not correct for multiplicity.

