## Section 4: Trial population

### Eligibility, inclusion, and exclusion

Inclusion and exclusion criteria are defined in detail in the Face-it trial protocol.

Eligibility and inclusion criteria:

- Women with a GDM diagnosis when attending or giving birth at one of the three recruiting hospitals. According to Danish guidelines, GDM is diagnosed when, following a 75 g oral glucose tolerance test (OGTT), the 2 h value is  $\geq 9.0$  mmol/l (venous plasma or capillary blood)
- Live in either Aarhus, Copenhagen, or Odense municipalities
- Able to understand and provide written informed consent in Danish

Exclusion criteria:

- Concomitant participation in other postpartum intervention
- Overt diabetes at baseline

The flow chart of the trial will comply with the CONSORT guidelines and will include the number of individuals who a) were invited during pregnancy b) consented to participate in the trial, c) attended baseline examination, d) were randomised at baseline, e) were lost to follow-up and f) were analysed for follow-up.

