### *Tertiary outcomes*

The treatment effect will be given as the baseline corrected difference between the groups at V2.

- Waist circumference (cm)
- Hip circumference (cm)
- Body fat%
- Weight change%
  
- 2h glucose (mmol/L)
- HbA1c (mmol/mol)
- Impaired Fasting Glucose (n and %)
- Impaired Glucose Tolerance (n and %)
- Fasting insulin (pmol/L)
- 2h insulin (pmol/L)
- HOMA-IR
- HOMA- $\beta$
- Systolic blood pressure (mmHg)
- Diastolic blood pressure (mmHg)
- Total cholesterol (mmol/L)
- LDL cholesterol (mmol/L)
  
- SF12
  - Physical component score
  
- IPAQ-SF
  - Walk (min/day)
- Breastfeeding duration (months)
  
- Social support for Diet and Exercise
  - Encouragement Family scale (Diet)
  - Participation Family scale (Exercise)
  -
- TSRQ Exercise self-regulation and motivation
  - Autonomous scale score
- General self-efficacy
- RPS-DD Risk perception
  - Perceived risk of getting diabetes, Moderate/high (n and %)
  - Made behaviour changes to change risk of diabetes, Yes (n and %)
  
- HLQ Health literacy
  - Domain 3 Actively engage my health
  - Domain 6 Ability to actively engage with healthcare providers

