## Analysis methods

### *Analysis population*

The primary analysis is an intention-to-treat analysis (ITT) including all participants who will be analysed as randomised.

Prior to further analyses and unblinding, all variables will be inspected to detect outliers to identify potential data entry errors.

Descriptive statistics will be summarised by randomisation group (see Section 4, Baseline characteristics).

The intervention effect for the primary outcomes will be estimated as the difference in BMI by randomisation group adjusted for BMI at baseline as well as the difference in SF-12 mental component score by randomisation group adjusted for SF-12 mental component score at baseline analysed in mixed models. Intervention effect for secondary and tertiary outcomes will likewise be estimated as difference in the outcome by randomisation group adjusted for the outcome at baseline. Continuous outcomes will be analysed in mixed models with a random effect for hospital, categorical outcomes will be analysed in generalized linear mixed models (family binomial, link logit) with a random effect for hospital, and duration of breastfeeding will be analysed using Cox proportional hazards regression with robust variance estimates for clustering due to hospital.

Due to randomisation, baseline values will not be statistically tested between groups. Mean differences between the study groups will be analysed using analysis of covariance, adjusted for baseline levels. Study site will be included as a random effect in the mixed models. Sample size of the study was based to prove a difference in BMI of  $-1.0 \text{ kg/m}^2$  between the two randomisation groups ( $\text{SD } 2.5 \text{ kg/m}^2$ ,  $\alpha = 0.05$ , power 80%).

Between group differences will be null-hypothesis tested and presented with P-values. The following supplementary analyses are planned for the primary outcomes as well as the secondary and tertiary outcomes:

1. An analysis similar to the one described above but including the per-protocol analysis population only. We will carefully consider the findings from the ITT analysis when drawing conclusions based on the per-protocol analysis, including whether a potential statistically significant result of the per-protocol analysis may be due to selection or the intervention.

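### The Cox model for breastfeeding duration clusters its robust variance on only three hospitals, so its Wald 95% interval covers about 75% at best

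*SAP*

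**What the plan says.** Section 5 (Analysis methods) fixes the model: "duration of breastfeeding will be analysed using Cox proportional hazards regression with robust variance estimates for clustering due to hospital". Section 4 (Eligibility, inclusion, and exclusion) recruits women attending or "giving birth at one of the three recruiting hospitals", so there are three clusters. In Section 2 (Randomisation), "Women with prior GDM are the unit of randomisation" and "Randomisation was stratified on Centres: Odense, Aarhus, Copenhagen sites", with 2:1 allocation inside each centre. Section 3 (Confidence intervals and p-values) adds: "Wald-based 95% confidence intervals will be given for all reported estimates". No finite-cluster correction or t reference distribution is named.

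Breastfeeding duration is listed under Tertiary outcomes in Section 5. Section 3 says of that tier: "These outcomes are considered descriptive/explorative meaning no definite inferences can be made". On tests the SAP is not settled. Section 3 states that "P-values will be reported for estimates related to the primary outcome and secondary outcomes", which leaves tertiary outcomes out, while Section 5 says without restriction that between-group differences are tested and given P-values.

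**The concern.** A cluster-robust (sandwich) variance estimates the spread of the cluster score totals, so it is reliable only with many clusters. With three, it is biased downwards and very unstable, and the normal quantile of 1.96 allows for neither fault. The error is not conservative: the interval is usually too narrow, so the hazard ratio looks more precise than it is.

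At stake is the interval for breastfeeding, which Section 1 names as one of three behaviours the intervention promotes. Section 5 also plans supplementary analyses for tertiary outcomes. That makes up to six further intervals with the same fault: one per-protocol, one excluding users of glucose-lowering medication, two BMI strata and two partner strata (1 + 1 + 2 + 2 = 6). Any P-value for this outcome would share it.

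**Working it through.** **Inputs from the SAP.** Three hospitals (Section 4); individual randomisation, 2:1 within centre (Section 2); Wald 95% interval, hence quantile 1.96 (Section 3); 225 women analysed and 322 at baseline (Section 2, Sample size). Hospital shares are not given, so they are assumed below and shown as a range.

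**The plan's own figures.** The figure under test is the nominal 95% coverage. The sample size serves only to set the size of the simulations, and it reproduces: a difference of 1.0, SD 2.5, two-sided 5%, 80% power and 2:1 give 74 + 148 = 222, against 225 stated. Power at 75/150 is 80.7%, and 225/0.7 = 321.4, rounded up to 322.

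**Form of the interval.** Let hospital g hold a share p_g of the information, scaled so that the total is 1. Its score is U_g, with variance p_g, and S is the sum of the three scores. The estimation error is proportional to S. After fitting, the hospital residual is R_g = U_g - p_g S. The three residuals sum to zero and are independent of S. The clustered Wald statistic is S / sqrt(sum of R_g^2).

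**Equal hospitals.** The sum of R_g^2 is distributed as one third of a chi-square with 2 degrees of freedom. Its mean is 2/3, where the true variance is 1. The statistic is therefore sqrt(3/2) times a t variable with 2 degrees of freedom, for which P(|t| < x) = x / sqrt(2 + x^2).

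- As planned: x = 1.96 / sqrt(1.5) = 1.600, so coverage = 1.600 / sqrt(2 + 2.561) = 1.600 / 2.136 = **74.9%**.
- With a G/(G-1) = 3/2 factor: 1.96 / sqrt(2 + 3.842) = 1.96 / 2.417 = **81.1%**.

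**Uneven hospitals.** Coverage is P(Z^2 < 1.96^2 Q), where Q is the quadratic form with the eigenvalues of diag(p) - pp'. A grid over all whole-percent splits has its maximum, 74.9%, at 34/33/33. The last column gives the range over full Cox simulations of the uncorrected clustered interval.

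| Split (assumed) | As planned, limit | With G/(G-1), limit | Cox simulation, as planned |
|---|---|---|---|
| Equal | 74.9% | 81.1% | 74.6-76.7% |
| 50/30/20 | 73.4% | 79.7% | 72.7-74.8% |
| 60/25/15 | 71.1% | 77.7% | 70.6-72.3% |
| 67/20/13 | 69.0% | 75.8% | 68.4-68.5% |
| 70/20/10 | 67.3% | 74.3% | 66.7-68.5% |
| 80/11/9 (extreme) | 61.9% | 69.3% | 62.0-62.1% |

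**Simulation settings.** There were two independent sets, each with 6,000 trials per setting and 2:1 allocation within hospital. Everything else is assumed:

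- Set 1: exponential durations at 0.03 per week, censoring at 52 weeks, hazard ratio 1, hospital log-hazard SD 0 or 0.3.
- Set 2: exponential durations with median 7 months, censoring at 12 months, log hazard ratio 0 or -0.3, and hospital log-hazard SD 0.2 in two of the settings.

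Totals were 225 or about 322. The Monte Carlo error of a clustered figure is about 0.6 points. A subgroup of 75 women (25 per hospital), run under set 1, gave 75.2-75.6%. In set 1 the median ratio of clustered to stratified standard error was 0.56-0.68, and 0.46-0.48 at 180/24/21.

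**Without the clustering (set 1, all settings).** Cox stratified by hospital with model-based errors covered 94.4-95.6%. Unstratified Cox covered 94.4-96.0% with model-based errors and 94.3-95.9% with individual-level robust errors. Set 2 gave 94.5-95.5% and 94.5-95.4% for the two unstratified versions.

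**The case against.** The case against is about weight and precision; the mechanism is not in dispute.

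- *The outcome is exploratory.* This stands as a limit on importance. No hierarchy, success rule or sample size depends on it. But the exploratory label waives multiplicity correction; it does not excuse a stated 95% interval that misses about one time in four. For a descriptive outcome the interval is the main information.
- *The software might apply a correction.* The SAP names none, and G/(G-1) reaches only 81.1% at best.
- *Hospital shares are unknown.* True, and mild imbalance matters little: 50/30/20 costs 1.5 points. The equal-hospital figure needs no assumed shares. It is a large-sample limit, not a strict ceiling at this sample size: one simulated equal-hospital setting gave 76.7%, about three Monte Carlo errors above it. Other runs with 75 women per hospital gave 74.6-76.2%, so that value is best read as noise.
- *The treatment effect may differ between hospitals.* Delivery did vary by area (Section 3, COVID-19 changes). In simulations with hospital-specific effects, the stratified model kept 95% coverage for the average over these three hospitals. For the mean of a wider population of hospitals its coverage fell to 94%, 89% and 81% at assumed between-hospital SDs of 0.1, 0.2 and 0.3 on the log hazard ratio. The qualification is fair, but that wider mean is not what this trial estimates, and the planned clustering covered only about 75% throughout.
- *Stratifying is a preference.* Agreed. Only removing the clustering is essential.

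**Conclusion.** The concern holds. As written, the nominal 95% interval for the breastfeeding hazard ratio covers about 75% with three equal hospitals and less if they are uneven. If a P-value is given, its type I error is about 25% (100 - 74.9 = 25.1) instead of 5%. The equal-hospital figure rests on the uncorrected sandwich variance with a normal quantile, which is what the SAP describes, and on large-sample theory that the simulations support at 225 and 322 women. The figures for uneven hospitals also rest on assumed shares. The statement that coverage returns to about 95% without clustering applies to a common treatment effect or to the average over these three hospitals. The scope is one tertiary outcome and its supplementary analyses.

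**What to change.** Delete the hospital-clustered variance from the sentence on breastfeeding in Section 5. Suggested replacement: *Breastfeeding duration will be compared between groups by a Cox model stratified by hospital, with model-based standard errors.* Stratifying follows the stratified randomisation. An unstratified Cox model with model-based or individual-level robust errors would also do. Use the same specification in the supplementary analyses of this outcome, and state whether tertiary outcomes receive P-values, since Sections 3 and 5 differ.

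Keeping the clustering and adding only G/(G-1) would not be enough, as the 81.1% shows. The cost is one line in the SAP and one in the code, with no new data, no extra analysis and no change to the analysed population.

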### Sample size

Calculation of the projected sample size is based on individual changes in BMI among women with prior GDM after 12 months of follow-up. The mean changes are compared between the intervention and usual care group. We expect the mean change in the intervention group to differ by  $-1.0 \text{ kg/m}^2$  relative to the usual care group. The standard deviation of individual changes after 12 months is expected to be  $2.5 \text{ kg/m}^2$ . Based on a 2:1 randomisation procedure, a power of at least 80% and type 1 error of 5% (two-sided), a sample size of 225 will be required to detect such a difference in BMI. Assuming 30% of participants will be lost between baseline (after randomisation) and follow-up, we will need to include 322 women at baseline in the study. Because of the relatively long period (10–30 weeks) between recruitment and baseline and the exclusion of women with overt diabetes at baseline (before randomisation), we also assume that 30% of those agreeing to participate will withdraw before baseline data collection or be excluded (see section 4) before randomisation. We therefore need to recruit 460 women. For full details of the sample size calculation, please refer to Face-it trial protocol (2).

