2. A sensitivity analysis, including the ITT analysis population, assessing the impact of missing data for the primary outcome. This analysis will only be performed in the case of a loss-to-follow-up rate  $> 10\%$ , i.e., more than 10% of all participants are missing at V2.
3. A sensitivity analysis excluding participants reporting use of glucose lowering medication at baseline.
4. A subgroup analysis stratified according to baseline BMI i)  $<25\text{kg/m}^2$  and ii)  $\geq 25\text{kg/m}^2$ .
5. A subgroup analysis stratified according to i) partner participation (defined as having a partner participating in the baseline visit) and ii) no partner participation (defined as not having a partner participating in the baseline visit).

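### Subgroup analyses 4 and 5 compare treatment within strata but plan no group × subgroup interaction, so the SAP neither estimates nor tests whether the effect differs between strata

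*SAP*

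**What the plan says.** SAP Section 5, Analysis methods, ends with five numbered supplementary analyses. Item 4 is "A subgroup analysis stratified according to baseline BMI", with a cut at 25 kg/m². Item 5 is "A subgroup analysis stratified according to i) partner participation" versus none, defined by whether a partner took part in the baseline visit.

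The list is introduced with "The following supplementary analyses are planned for the primary outcomes as well as the secondary and tertiary outcomes". The sentence just before it reads "Between group differences will be null-hypothesis tested and presented with P-values".

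Section 3 (Confidence intervals and p-values) adds two general rules: "P-values will be reported for estimates related to the primary outcome and secondary outcomes", and "Wald-based 95% confidence intervals will be given for all reported estimates". Its multiplicity text covers the two outcome hierarchies and does not mention subgroups.

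Nowhere does the SAP mention an interaction term, a heterogeneity test or a contrast between strata. Item 1 (per-protocol) comes with guidance on how to read its result against the ITT analysis; items 4 and 5 have none.

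**The concern.** A subgroup analysis is done to learn whether the treatment effect differs between types of women. Two separate within-stratum comparisons do not answer that. Each asks only whether the effect in its own stratum differs from zero, with fewer women than the trial was sized for.

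When the overall trial has about 80% power, a single stratum has much less. One stratum will then often reach significance while the other does not, even if the true effect is the same in both. A report with such a split, and no planned estimate of the difference, invites the reading that the intervention works in one group of women and not in the other. At stake is how the supplementary results are read, not the primary result.

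**Working it through.** **Inputs from the SAP (Section 2, Sample size).** Effect −1.0 kg/m², SD of change 2.5 kg/m², 2:1 allocation, two-sided 5%, power at least 80%; "a sample size of 225 will be required to detect such a difference in BMI"; and, after 30% loss, "we will need to include 322 women at baseline in the study".

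**Assumptions not in the SAP.** Stratum shares from 50:50 to 20:80, 2:1 allocation within each stratum, and the same true effect in both strata. An SD of 2.0 is used as a sensitivity value for the gain from baseline adjustment.

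**Reproducing the plan's figure.** Usual-care n = (1.960 + 0.842)² × 2.5² × (1 + 1/2) / 1.0² = 73.6, so 74, and 3 × 74 = 222 in total, close to the stated 225. With 75 and 150 women, SE = 2.5 × √(1/75 + 1/150) = 0.354, and power is 80.4% by the noncentral t. Also 225 / 0.70 = 321.4, so 322. The design figures hold.

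**Power within a stratum.** With n women split 2:1, SE = SD × √(3/n + 1.5/n) = SD × √(4.5/n). For example, n = 112.5 gives 2.5 × √0.04 = 0.50, and n = 45 gives 2.5 × √0.10 = 0.79.

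**Exactly one stratum significant.** The strata contain different women, so the two tests are independent and P = p₁(1 − p₂) + p₂(1 − p₁).

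**Interaction.** SE = SD × √(4.5/n₁ + 4.5/n₂), and the 95% half-width is about 1.97 × SE.

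Results for 225 women and SD 2.5:

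| Split | Stratum power at −1.0 | Exactly one significant, −1.0 | Exactly one significant, −0.5 | Interaction SE | Half-width | Interaction power, difference 1.0 |
|---|---|---|---|---|---|---|
| 50:50 | 0.509 / 0.509 | 0.500 | 0.279 | 0.707 | 1.39 | 0.291 |
| 30:70 | 0.333 / 0.652 | 0.551 | 0.285 | 0.772 | 1.52 | 0.252 |
| 20:80 | 0.235 / 0.711 | 0.612 | 0.291 | 0.884 | 1.74 | 0.203 |

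Worked line for 20:80: 0.235 × 0.289 + 0.711 × 0.765 = 0.068 + 0.544 = 0.612.

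With no effect in either stratum: 2 × 0.05 × 0.95 = 0.095, whatever the split.

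Sensitivity of the −1.0 column (exactly one stratum significant):

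| Analysed, SD | 50:50 | 30:70 | 20:80 |
|---|---|---|---|
| 322, SD 2.5 | 0.447 | 0.530 | 0.628 |
| 225, SD 2.0 | 0.422 | 0.514 | 0.623 |
| 322, SD 2.0 | 0.263 | 0.385 | 0.536 |

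Outside the assumed shares, a 10:90 split with 225 women and SD 2.5 gives about 0.69.

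With 322 women and SD 2.5, interaction power for a 1.0 kg/m² difference is 0.392 / 0.340 / 0.271, with half-widths of 1.16 / 1.27 / 1.45.

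No figure is given for the SF-12 mental component because the SAP states neither an effect size nor an SD for it.

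**The case against.** **No comparison of stratum p-values is planned.** A reader might infer that the plan has a 50–61% rate of false subgroup claims, against 5% for an interaction test. The SAP does not support this. It never says that a difference in significance will be taken as a difference in effect, so the percentages describe how often a pattern appears and not the error rate of a stated rule. This part of the objection stands in full.

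**The percentages are not bounds.** They depend on assumed shares, on the number analysed and on the SD. That also stands, so the sensitivity values belong beside the headline range.

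**The p-value sentence may describe only the main analysis.** It stands before the supplementary list, and Section 3 limits p-values to primary and secondary outcomes. The point survives either way. The SAP promises 95% CIs for all estimates, and one interval excluding zero beside one that does not shows the same split.

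**The stratum CIs let a reader work out the difference.** For continuous outcomes this is roughly true, but it is not a prespecified estimate. Similarly, stratifying does not rule out getting both stratum effects from one model with an interaction, but the SAP does not say this will be done.

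**Existing safeguards.** The analyses are called supplementary, tertiary outcomes are declared descriptive, and a primary claim needs supporting size, direction and CI. These limit the harm. None of them says how a difference between strata is to be judged.

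**Number of tests.** A reader might multiply 38 outcomes by four strata and add a multiplicity charge. That is a separate matter. It turns on how the two p-value statements are reconciled, and adding an interaction would not cure it.

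**Low power of the interaction.** This is true: the half-width exceeds the design effect of 1.0 kg/m². But the stratified plan rests on the same information and leaves the imprecision unstated.

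**Conclusion.** The point holds as an omission with a cheap remedy. Items 4 and 5 plan within-stratum comparisons and nothing that estimates or tests the difference between strata.

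For BMI with 225 analysed, 2:1 allocation, SD 2.5 and assumed shares of 50:50 to 20:80, a uniform effect of −1.0 kg/m² gives a one-stratum-only result in about 50–61% of trials. Across 225–322 women and SDs of 2.0–2.5 the range is 26–63%. It is about 69% at a 10:90 split (225 women, SD 2.5), 28–29% at an effect of −0.5 (225 women, SD 2.5), and 9.5% with no effect.

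These are chances of a misleading pattern. They do not show that the sponsor intends to misread it, and the primary analyses are untouched. The change should be made before the analysis, but the trial's main conclusions do not depend on it.

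**What to change.** Reword items 4 and 5 as follows:

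- Fit the planned baseline-adjusted mixed model, with its random effect for site, to all ITT women. Add the subgroup main effect and a randomisation group × subgroup term. In the BMI model, keep continuous baseline BMI as covariate beside the indicator for 25 kg/m² or more.
- Limit formal interaction tests to the two primary outcomes: 2 outcomes × 2 factors = 4 tests.
- Base any claim of a differential effect only on the interaction estimate with its 95% CI and p-value.
- Show stratum effects with 95% CIs and without p-values for every outcome, including BMI and the SF-12 mental component. Intervals can still look split, so the preceding rule is what prevents a wrong reading.
- Label all subgroup results exploratory.

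The cost is two model terms per factor and some SAP wording; no new data are needed. The drawback is low power: about 20–29% for a 1.0 kg/m² difference with 225 women (half-width 1.4–1.7 kg/m²), or 27–39% if all 322 are analysed (SD 2.5 in both). The report should therefore state that a non-significant interaction does not show a uniform effect.
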